## 4.8. Interim Analyses

## **4.8.1. Data Monitoring Committee (DMC)**

An independent external DMC will be responsible for reviewing unblinded data during the study. The committee will include 4 clinicians and 1 statistician who are independent experts not involved in the study. The DMC will review unblinded safety data to ensure the safety of study participants and some efficacy data to confirm a reasonable risk-benefit profile. A subset of analyses described above in Sections 4.3 to 4.6 will be provided for the DMC review. The external Statistical Analysis Center statistician/analyst will generate the unblinded reports and confidentially distribute the unblinded reports to DMC members. Study team will remain blinded to study treatment until the planned unblinding occurs. The DMC will be conducted to maintain study integrity. Details of the DMC are included in the DMC charter.

## 4.9. Changes to Protocol-Planned Analyses

There are no changes but additional details are provided to the analyses described in the protocol.

## 5. Sample Size Determination

Approximately 670 participants will be randomly assigned to LY3209590 and insulin glargine in a 1:1 ratio.

With the assumption of 15% dropout at Week 52 (Visit 33), approximately 284 participants on LY3209590 and 284 participants on insulin glargine will complete 52 weeks of treatment.

The number of completers will provide at least 99% statistical power to show noninferiority between LY3209590 and insulin glargine using the upper limit of a 2-sided 95% CI and these assumptions:

- NIM of 0.4%
- no true difference between treatment groups, and
- an SD of 1.1%.

This sample size has at least 90% statistical power to show noninferiority between LY3209590 and insulin glargine using a 0.3% NIM at Week 52 (Visit 33).

The number of completers will provide 90% statistical power to show superiority between LY3209590 and insulin glargine for change in HbA1c from baseline to Week 52 (Visit 33), assuming an SD of 1.1% and true mean difference of -0.3%, and alpha of 0.05.

## 6. Supporting Documentation

## 6.1. Appendix 1: Demographic and Baseline Characteristics

Demographic and baseline characteristics including but not limited to age (years), age groups ( $<65, \ge 65$  and  $<75, \ge 75$  and  $<85, \ge 85$  years), sex, ethnicity, race, country, region, height, weight (kg), BMI (kg/m2), BMI groups ( $<25, \ge 25$  and  $<30, \ge 30$  and  $<35, \ge 35$  kg/m²), eGFR groups ( $<30, \ge 30$  and  $<60, \ge 60$  and  $<90, \ge 90$  mL/min/1.73 m²), duration of diabetes (years), HbA1c at screening, HbA1c stratum at screening (<8.0% and  $\ge 8.0\%$ ), baseline HbA1c, baseline HbA1c stratum (<8.0% and  $\ge 8.0\%$ ), fasting serum glucose (mmol/L and mg/dL), GLP-1 RA treatment at randomization, and number of non-insulin antihyperglycemic medications in use at randomization will be summarized by treatment group using the mITT and Randomized Population (if different from the mITT).

Continuous measures will be summarized using descriptive statistics and treatment difference will be analyzed using the analysis of variance. Categorical measures will be summarized using sample size, frequency, and percentage and treatment difference will be analyzed using Chi-squared test.

The by participant listing of demographic and baseline characteristics will be provided for Randomized Population.

Historical conditions are conditions that end prior to inform consent and preexisting conditions are conditions that are still ongoing at inform consent. The number and percentage of participants with historical conditions will be summarized by treatment group using MedDRA PT using the mITT and Randomized Population (if different from the mITT). Events will be ordered by decreasing frequency within SOC. Similar summary will also be provided for preexisting conditions.

# **6.2.** Appendix 2: Treatment Compliance

Treatment compliance will be summarized using the mITT population excluding Inadvertently enrolled participants.

The study protocol provides dosing algorithms for both study treatments. The investigator will calculate the algorithm recommended dose based on participant's fasting blood glucoses and hypoglycemia occurrence reported in e-diary. If the investigator does not agree with the algorithm recommended dose, the investigator will prescribe another dose for the participant and choose a reason for not following the algorithm recommended dose from a picklist. The number and percentage of investigator prescribed doses different from algorithm recommended doses will be provided to evaluate investigator's adherence to the dosing algorithm. The reasons for not following the algorithm recommended dose will also be summarized. The number and percentage of investigator prescribed doses that are not equal to participant administered dose will also be provided.

## 6.4. Appendix 4: Concomitant Medication

Concomitant therapy is defined as the therapy that starts before, on, or after the first day of study treatment and before the last dose date in the treatment period, and continues into the treatment period, that is, either no end date (the therapy is ongoing) or an end date on or after the first day of study treatment.

The number and percentages of participants who take concomitant medication will be summarized by treatment using PTs nested within ATC Level. The concomitant medications will be ordered by decreasing frequency of LY3209590 within each ATC level.

## 6.5. Appendix 5: Protocol Deviations

IPDs are the deviations from the study protocol that may compromise the data integrity and patients' safety. The IPD category and details of IPD identification are provided in the trial issue management plan.

The number and percentage of participants with any reported IPDs will be summarized by treatment group and IPD category. The IPDs identified by site monitoring and clinical database will be integrated. If the IPD is identified by both methods, only the site monitoring IPD will be presented.

## 6.6. Appendix 6: MedDRA PT for Diabetic Retinopathy or Maculopathy

The following PTs will be used to identify TEAEs of diabetic retinopathy or maculopathy (see Section 4.6.2.1.7):

- Amaurosis
- Amaurosis fugax
- Arteriosclerotic retinopathy
- Blindness
- Blindness transient
- Blindness unilateral
- Choroidal neovascularisation
- Cystoid macular oedema
- Detachment of macular retinal pigment epithelium
- Detachment of retinal pigment epithelium
- Diabetic blindness
- Diabetic eye disease
- Diabetic retinal oedema
- Diabetic retinopathy
- Diabetic uveitis
- Diplopia
- Exudative retinopathy
- Eye laser surgery
- Fundoscopy
- Fundoscopy abnormal
- Intra-ocular injection
- Macular detachment
- Macular oedema
- Maculopathy
- Noninfective chorioretinitis
- Noninfective retinitis
- Phacotrabeculectomy
- Retinal aneurysm
- Retinal arteriovenous malformation
- Retinal artery embolism
- Retinal artery occlusion
- Retinal artery stenosis
- Retinal collateral vessels
- Retinal cryoablation
- Retinal detachment
- Retinal exudates
- Retinal haemorrhage
- Retinal laser coagulation
- Retinal neovascularisation
- Retinal oedema

- Retinal operation
- Retinal thickening
- Retinal vascular disorder
- Retinal vascular occlusion
- Retinal vein occlusion
- Retinitis
- Retinopathy
- Retinopathy haemorrhagic
- Retinopathy hypertensive
- Retinopathy hyperviscosity
- Retinopathy proliferative
- Scintillating scotoma
- Sudden visual loss
- Venous stasis retinopathy
- Vision blurred
- Visual acuity reduced
- Visual acuity reduced transiently
- Visual impairment
- Vitrectomy

# 6.7. Appendix 7: MedDRA PT for Peripheral Edema

The analysis of peripheral edema (Section 4.6.2.1.8) will be based on the TEAEs in the following terms:

- Acute pulmonary oedema
- Ascites
- Brain oedema
- Bronchial oedema
- Capillary leak syndrome
- Cerebral oedema management
- Compression garment application
- Cytotoxic oedema
- Effusion
- Fluid retention
- Gastrointestinal oedema
- Generalised oedema
- Gravitational oedema
- Hydraemia
- Hypervolaemia
- Hypoosmolar state
- Lipoedema
- Lymphoedema
- Negative pressure pulmonary oedema
- Non-cardiogenic pulmonary oedema

- Non-pitting oedema
- Oedema
- Oedema blister
- Oedema due to cardiac disease
- Oedema due to hepatic disease
- Oedema due to renal disease
- Oedema mucosal
- Oedema peripheral
- Pelvic fluid collection
- Pericardial effusion
- Perinephric collection
- Perinephric oedema
- Peripheral swelling
- Pleural effusion
- Pulmonary oedema
- Retroperitoneal effusion
- Retroperitoneal oedema
- Skin oedema
- Skin swelling
- Subdural effusion
- Swelling
- Visceral oedema

## 6.8. Appendix 8: Empirical Estimation of Relative Event Rate

Traditionally, Poisson distribution has been assumed to draw inference for the rate of rare events. When the event is rare and the sample size is large, it is known that the overall number of events is approximately from Poisson distribution. However, for some not very rare events such as severe hypoglycemic events in T2D patients, the total number of events may not be distributed from Poisson and may be over-dispersed. Assuming Poisson distribution may significantly underestimate the variance, and therefore may reduce the overage probability and inflate the type I error. An empirical method in estimating the variance of the relative event rate without assuming any distribution on the number of events will be provided in this appendix.

Let  $X_{ij}$  denote the count response variable for patient j in treatment group i. Let  $Y_i = \sum_j X_{ij}$  be the total number of events for treatment group i, and  $T_i$  denote the exposure for treatment group i. Let i = 0 for the control group and i = 1 for the experimental treatment group. The event rate for treatment group i can be calculated as

$$\hat{r}_i = \frac{Y_i}{T_i}$$

The empirical variance of  $\hat{\mathbf{r}}_i$  is

$$\widehat{Var}(\hat{r}_i) = T_i^{-2} \widehat{Var}(Y_i) = T_i^{-2} n_i S_i^2,$$

where  $S_i^2$  is the variance of  $X_{ij}$  for treatment group *i*. Using the delta-method, the variance of  $\log(\hat{r}_i)$  can be estimated as

$$\widehat{Var}(\log(\hat{r}_i)) = Y_i^{-2} n_i S_i^2$$

The relative rate of the experimental treatment versus the control treatment is estimated as

$$\hat{\lambda} = \frac{\hat{r}_1}{\hat{r}_0}$$

The variances of  $\hat{\lambda}$  and  $\log(\hat{\lambda})$  are

$$\widehat{Var}(\widehat{\lambda}) = \widehat{\lambda}^2 \widehat{Var}(\log(\widehat{\lambda}))$$

$$\widehat{Var}\left(\log\left(\hat{\lambda}\right)\right) = \widehat{Var}(\log(\hat{r}_0)) + \widehat{Var}(\log(\hat{r}_1)) = Y_0^{-2}n_0S_0^2 + Y_1^{-2}n_1S_1^2$$

Assuming  $\log(\hat{\lambda})$  is asymptotically from a normal distribution, the  $100(1-\alpha)\%$  confidence interval for  $\log(\hat{\lambda})$  can be constructed as

$$\left[\log(\hat{\lambda}) - z_{1-\frac{\alpha}{2}} \sqrt{\widehat{Var}(\log(\hat{\lambda}))}, \log(\hat{\lambda}) + z_{1-\frac{\alpha}{2}} \sqrt{\widehat{Var}(\log(\hat{\lambda}))}\right]$$

Then, the  $100(1-\alpha)\%$  confidence interval for  $\hat{\lambda}$  is

$$\left[\hat{\lambda} \exp\left(-z_{1-\frac{\alpha}{2}}\sqrt{\widehat{Var}(\log(\hat{\lambda}))}\right), \qquad \hat{\lambda} \exp\left(z_{1-\frac{\alpha}{2}}\sqrt{\widehat{Var}(\log(\hat{\lambda}))}\right)\right] \tag{1}$$

The p-value for testing the null hypothesis of  $H_0$ :  $\lambda = 1$  is calculated as

$$p = 2\Phi\left(\left|\log(\hat{\lambda})\right| / \sqrt{\widehat{Var}(\log(\hat{\lambda}))}\right)$$
 (2)

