# Hypoglycemia analysis

The analysis periods of 0-16, 0-26, 0-52, 16-26, and 26-52 weeks of treatment will be considered.

The participant-reported hypoglycemia will be analyzed using data from the e-diary by

- Level 1 (glucose  $\geq$ 54 to <70 mg/dL)
- Level 2 (glucose <54 mg/dL)
- Level 3 (severe), and
- the composite of Levels 2 and 3.

This table gives definitions for documented hypoglycemia events.

Documented hypoglycemia	Definition
All documented hypoglycemia	episodes for the 24-hour period
Non-nocturnal hypoglycemia	episodes during 0600 hours to midnight
Nocturnal hypoglycemia	episodes during midnight to 0600 hours

The incidence and rate of hypoglycemia will be summarized by treatment and analysis period for different types of hypoglycemia.

For continuous safety variables, such as laboratory measures, vital signs and weight, MMRM or ANCOVA models will be used.

For categorical safety variables, such as AEs, incidence of hypoglycemia, and treatmentemergent abnormal laboratory measurements, either Fisher's exact test or logistic regression will be used for treatment comparison.

Further details for assessing all safety measures will be provided in the SAP.

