For continuous measures, summary statistics will include sample size, mean, SD, median, minimum, and maximum for both the actual and the change from baseline measurements. For certain variables that are considered to be log-normally distributed, the geometric mean and CV will be provided instead. Either the mixed model repeated measurement (MMRM) model or the analysis of covariance (ANCOVA) model will be used to analyze continuous outcomes. LS means and standard errors derived from the analysis models will also be displayed. Treatment comparisons will be displayed showing the treatment difference LS means and the 95% CIs for the treatment differences, along with the p-values for the treatment comparisons. For certain safety laboratory measures, log-transformed values will be analyzed in the statistical model instead. The actual change from baseline and percentage change from baseline will be presented using the derivation based on the output from the statistical model and the assumption of lognormality.

For categorical measures, summary statistics will include sample size, frequency, and percentages. Fisher's exact test or logistic regression will be used for treatment comparisons, unless otherwise stated. For laboratory values, both CN and SI units will be presented. Therefore, both % and mmol/mol will be presented for HbA1c and both mg/dL and mmol/L will be presented for glucose measurements.

In this study, the negative binomial regression will be used to analyze the number of hypoglycemic episodes. Group Mean instead of LS mean will be estimated and delta method will be used to estimate the standard error of the Group Mean (Qu and Luo 2015). Group Mean is defined as the mean response in the treatment group for the studied population. The difference between LS mean and the Group Mean is that LS mean estimates the response by taking the

inverse link function on mean covariates, while the Group Mean takes the inverse link function on individual patient covariates first and then averages over all patients. For Level 2 hypoglycemia and severe hypoglycemia, the empirical method based on exposure-adjusted rate (calculated by total number of events divided by total exposure) may be used for the treatment comparison if the number of episodes is too small and leads to convergency issues in the negative binomial regression model.

Below table describes the definition of baseline and postbaseline observations for different analyses.

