		Appendix 8 [Section 6.8] for
		details) will be used for treatment
		comparison.
Event rate of Level 3	Baseline, 0-26, 0-52, 26-52 weeks,	Negative binomial regression with
hypoglycemia events	post-treatment period	treatment and baseline HbA1c as
(events/participant/100 year):		covariates, log (exposure/36525
All documented		days) as the offset in the model.
		If the number of events is too small
		to run the negative binomial
		regression, exposure-adjusted rate
		calculated by total number of events
		divided by total exposure for
		individual patients will be provided
		and the empirical method (see

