		Appendix 8 [Section 6.8] for
		details) will be used for treatment
		comparison.
		The plots of the mean cumulative
		functions (MCFs) by each treatment
		arm will also be created. The
		population mean for cumulative
		number of events up to time $t$ , $M(t)$ ,
		will be estimated using a
		nonparametric estimation method
		described by Nelson (2003).
Incidence of Level 1	Baseline, 0-16, 0-26, 0-52, 16-26,	Logistic regression with treatment
hypoglycemia events:	26-52 weeks, post-treatment period	and baseline HbA1c as covariates.
All documented		
Incidence of Level 2	Baseline, 0-16, 0-26, 0-52, 16-26,	Logistic regression with treatment
hypoglycemia events:	26-52 weeks, post-treatment period	and baseline HbA1c as covariates.
All documented		
Incidence of Level 3	Baseline, 0-26, 0-52, 26-52 weeks,	Logistic regression with treatment
hypoglycemia events:	post-treatment period	and baseline HbA1c as covariates.
All documented		
Incidence of Level 2/3	Baseline, 0-16, 0-26, 0-52, 16-26,	Logistic regression with treatment
hypoglycemia events:	26-52 weeks, post-treatment period	and baseline HbA1c as covariates.
All documented		
Nocturnal		
Non-nocturnal		

Endpoint	Analysis Period*	Statistical Method
Potential persistent-recurrent	Safety analysis period (see	The number of participants with at
hypoglycemia events	definition in Section 4.6)	least one event will be summarized

 
identified by
 
		and compared by Fisher's exact test.
investigator		The number of events will also be

 
identified by pre-
 
		provided.
criteria (defined in		
Appendix 9		
[Section 6.9])		

Abbreviations: HbA1c = hemoglobin A1c; Level 2/3= Level 2 and Level 3 composite; mITT = modified Intent-to-Treat.

Note: The hypoglycemia yearly rate during defined period is calculated by the number of hypoglycemia within the period/number of days patient at risk within the period times 365.25. For rare events, 100-year rate will be provided. The hypoglycemia incidence during defined period indicates if the patient has at least 1 hypoglycemia events within the period (Yes/No).

A sensitivity analysis will be done for selected hypoglycemic endpoints where all hypoglycemic events are considered one hypoglycemic event until a subsequent glucose value is  $\geq 70 \text{ mg/dL}$ .

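### SAP Appendix 8, the fallback for sparse hypoglycemia rates, gives no confidence interval or p-value when an arm has zero Level 3 events, and no rule says what then replaces the comparison

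*SAP*

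**What the plan says.** SAP Section 4.1 plans negative binomial regression for the number of hypoglycemic episodes. For Level 2 and severe hypoglycemia it adds that "the empirical method based on exposure-adjusted rate (calculated by total number of events divided by total exposure) may be used for the treatment comparison" if too few episodes cause convergence problems. The table in SAP Section 4.6.3.1 repeats this fallback for the Level 2, Level 3 and Level 2/3 rates and points to Appendix 8. No minimum event count is given. For Level 3 the table lists the periods "Baseline, 0-26, 0-52, 26-52 weeks" and the post-treatment period.

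Appendix 8 (SAP Section 6.8) describes itself as "An empirical method in estimating the variance of the relative event rate without assuming any distribution on the number of events". Its variance for the log rate in arm i is "Var}(\log(\hat{r}_i)) = Y_i^{-2} n_i S_i^2". The variance of the log rate ratio is the sum of the two arm terms. Confidence interval (1) and p-value (2) are both built on that sum.

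For Level 3 incidence, the same table gives "Logistic regression with treatment" and baseline HbA1c as covariates, and nothing else. The general text is wider. For categorical measures, SAP Section 4.1 says that Fisher's "exact test or logistic regression will be used for treatment comparisons, unless otherwise stated". The protocol's hypoglycemia analysis text likewise says that either Fisher's "exact test or logistic regression will be used for treatment comparison".

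**The concern.** Appendix 8 is there for sparse data, and an empty arm is the extreme of sparse data. In that case the negative binomial estimate of the log rate ratio also diverges, so the analysis would move to Appendix 8 and find no usable result there. For Level 3 incidence, a logistic model with a treatment term has no finite treatment estimate when one arm has no participant with an event.

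The incidence and rate of Level 3 events form a listed tertiary safety endpoint. If an arm is empty in a period, the planned rate comparison has no interval or p-value, the planned incidence model fails, and the team must choose a substitute that the SAP does not name.

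**Working it through.** **1. Algebra.** Appendix 8 defines Y_i as the sum of the participant counts X_ij, and S_i² as their variance.

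- If arm i has no events, every X_ij is 0, so Y_i = 0 and S_i² = 0. Then n_i S_i² / Y_i² = 0/0.
- The variance of the log ratio adds both arm terms, so one empty arm is enough to make it undefined.
- The ratio is 0 if only the LY3209590 arm is empty, a division by zero if only the glargine arm is empty, and 0/0 if both are. Its logarithm is not finite in any of these cases.
- With one event in each arm and 335 participants per arm, the formula works: variance 1 + 1 = 2, 95% CI 0.063 to 16.0. The failure is specific to an empty arm.

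**2. How often an arm could be empty.** The plan supplies 670 participants randomised 1:1 (335 per arm), 15% dropout and 52 weeks of treatment. Its completer figure reproduces: 335 × 0.85 = 284.75, stated as 284. The plan gives no Level 3 rate, so the rates below are assumptions, taken as equal in both arms.

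With dropout spread evenly over the year, patient-years per arm are:

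- weeks 0-52: 335 × (1 − 0.15/2) × 364/365.25 = 308.8
- weeks 0-26: 335 × (0.5 − 0.075 × 0.25) × 364/365.25 = 160.7
- weeks 26-52: 308.8 − 160.7 = 148.1

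For Poisson counts, the chance that a given arm is empty is q = exp(−rate × patient-years). The chance of at least one empty arm is 1 − (1 − q)².

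| Assumed rate per patient-year | Expected events per arm, 0-52 | 0-52 weeks | 0-26 weeks | 26-52 weeks |
|---|---|---|---|---|
| 0.002 | 0.6 | 79% | 92% | 93% |
| 0.005 | 1.5 | 38% | 70% | 73% |
| 0.01 | 3.1 | 9% | 36% | 40% |
| 0.02 | 6.2 | 0.4% | 8% | 10% |

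Example at 0.005 over 52 weeks: q = exp(−1.544) = 0.213, and 1 − 0.787² = 0.38.

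**3. Sensitivity, weeks 0-52.** If all dropout falls at the start (284 patient-years) or at the end (334), the four figures run 81-76%, 43-34%, 11-7% and 0.7-0.25%. With an assumed negative binomial dispersion of 20, q = (1 + 20 × rate × 308.8/335)^(−335/20), which gives 79%, 40%, 11% and 1.0%. Both arms are empty (q²) with chance 29%, 5%, 0.2% and under 0.01%.

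**4. Equation (2).** In the text available here it begins "p = 2\Phi\left(\left|\log(\hat{\lambda" and applies Φ to a non-negative argument, so the result lies between 1 and 2. Take six single events in control and one in LY3209590, with 335 per arm and equal exposure:

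- variance = 0.164 + 1.000 = 1.164, so SE = 1.079
- |log(1/6)| / 1.079 = 1.792 / 1.079 = 1.661
- 2Φ(1.661) = 1.903, whereas 2[1 − Φ(1.661)] = 0.097

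Interval (1) for the same data is 0.020 to 1.38, which is correctly formed.

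**The case against.** The strongest reply is that little is lost. SAP Section 4.6 makes Fisher's exact test with risk difference and 95% CI the default for safety comparisons. Section 4.6.2.1.1 plans a severe-hypoglycemia summary by risk difference and a listing. The Section 4.6.3.1 table still yields an exposure-adjusted rate for each arm. All of these work with zero events, and reporting a ratio as not estimable is ordinary practice. This stands, and it is why the point is minor. It does not close the gap: Fisher's test compares participants rather than rates, the Section 4.6 default covers treatment plus follow-up rather than each period, and the table row for Level 3 incidence specifies logistic regression.

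Four stronger readings are tempting, and the documents do not support them.

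- **That an empty arm is likely.** The high percentages come from assumed rates. Appendix 8 itself treats severe hypoglycemia in type 2 diabetes as not especially rare, which points to the low end. On the other side, the protocol excludes people with severe episodes in the 6 months before screening.
- **That the need for a substitute would show only after unblinding.** Protocol Section 8.3.6 requires severe events to be reported as SAEs, so a low pooled count can be seen while the team is blinded.
- **That the result turns on which substitute is chosen.** For 6 events against 0, an exact Poisson comparison gives p = 0.031, while adding 0.5 to each total gives a 95% CI for the ratio of 0.004 to 1.37. Both rest on the Poisson assumption that Appendix 8 sets out to avoid. Fisher's test remains among the methods the SAP names.
- **That the SAP contains a wrong p-value formula.** A minus sign may have been lost when the PDF was read.

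**Conclusion.** The point holds as a minor gap for Level 3 hypoglycemia. That the formula fails with an empty arm follows from Appendix 8 alone and needs no assumption. How often this would happen depends on the assumed rates: it is material at about 0.01 per patient-year or below and in the half-year periods, and negligible over 52 weeks at 0.02. The same fallback serves Level 2 and Level 2/3 rates, so a reader might extend the problem to them. Nothing in the documents shows a practical effect there, and none is claimed.

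The primary and gated HbA1c tests are unaffected. Level 3 is tertiary and outside the gatekeeping, and severe events would still be summarised and listed. Equation (2) is a matter to check against the source, not an established error.

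**What to change.** (a) In SAP Section 4.6.3.1 and Appendix 8, state the following for each analysis period.

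- If exactly one arm has zero events, report both exposure-adjusted rates and show the rate ratio, its CI and its p-value as not estimable. Compare participants with at least one event by Fisher's exact test, with risk difference and 95% CI, in place of logistic regression.
- If both arms have zero events, report descriptively with no test.

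(b) Check equation (2) against the source document. If it stands there as 2Φ(|log λ|/SE), replace it with 2[1 − Φ(|log λ|/SE)].

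The cost is a few sentences and minor programming, with no change to data collection. The downside is that in a period with an empty arm the inference is on participants with an event, not on event rates. A participant-level permutation test of the rate difference might seem to avoid this. It supplies no CI, however, and with equal exposure and one empty arm it gives the same p-value as Fisher's test, so it is not recommended.

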# 4. Statistical Analyses

#### 4.1. General Considerations

Statistical analysis of this study will be the responsibility of Eli Lilly and Company (Lilly) or its designees. Any change to the data analysis methods described in the protocol will require an amendment ONLY if it changes a principal feature of the protocol. Any other changes to the data analysis methods described in the protocol, and the justification for making the change, will be described in the SAP or the final clinical study report. Additional exploratory analyses of data will be conducted as deemed appropriate.

Unless otherwise stated, the efficacy analyses will be conducted on either EAS1 or EAS2. Primary and key secondary (gated) objectives will be based on both treatment regimen estimand and efficacy estimand, while the other secondary and tertiary efficacy measures will be based on efficacy estimand. For treatment regimen estimand, EAS1 (see the definition in Section 3) will be used for analysis. For efficacy estimand, other secondary and tertiary efficacy measures, EAS2 (see the definition in Section 3) will be used for analysis.

Unless otherwise noted, the safety analyses will be conducted on the SS. Percentages will be calculated using the mITT population as the denominator. For events that are sex-specific, the denominator and computation of the percentage will include only participants from the given sex.

All tests of treatment effects will be conducted at a 2-sided alpha level of 0.05 and 2-sided 95% CIs will be calculated.

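### The p-value formula in SAP Appendix 8, as printed, always lies between 1 and 2 and so contradicts the correct confidence interval beside it

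*SAP*

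**What the plan says.** SAP Section 4.1 plans negative binomial regression for the number of hypoglycemic episodes. For Level 2 and severe hypoglycemia it adds a fallback for when few episodes cause convergence problems: "the empirical method based on exposure-adjusted rate (calculated by total number of events divided by total exposure) may be used for the treatment comparison". The table in SAP Section 4.6.3.1 names the same fallback for the Level 2, Level 3 and Level 2/3 event rates and refers to Appendix 8 for the method.

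Appendix 8 defines the rate ratio λ̂ and takes the variance of its logarithm as "Y_0^{-2}n_0S_0^2 + Y_1^{-2}n_1S_1^2". It assumes that log(λ̂) "is asymptotically from a normal distribution" and gives two results:

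- Equation (1), a confidence interval for the rate ratio. Its lower limit contains "\lambda} \exp\left(-z_{1-\frac{\alpha}{2}}\sqrt{\widehat{Var}(\log(\hat{\lambda" (typesetting source, cut), with the minus sign present.
- Equation (2), introduced by "The p-value for testing the null hypothesis of" λ = 1, and printed as "p = 2\Phi\left(\left|\log(\hat{\lambda})\right| / \sqrt{\widehat{Var}(\log(\hat{\lambda" (cut before the closing brackets).

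Section 4.1 also sets the general rule: "All tests of treatment effects will be conducted at a 2-sided alpha level of 0.05 and 2-sided 95% CIs will be calculated".

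**The concern.** Equation (2) takes the normal distribution function of a non-negative number and doubles it. A two-sided p-value needs the upper tail beyond |z|, doubled. The printed formula has neither the complement (1 − Φ) nor a minus sign inside Φ, so it cannot return a value below 1.

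The fallback matters most where events are sparse, and severe hypoglycemia is the obvious case. The Level 2/3 composite rate, overall and nocturnal, is a listed secondary endpoint. A prespecified safety formula should be usable as written. Here a programmer would have to depart from the approved SAP or output an impossible number beside a valid interval.

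**Working it through.** **Inputs.** Equations (1) and (2), the variance formula and the normal approximation come from SAP Appendix 8. The two-sided 0.05 level and 95% intervals come from SAP Section 4.1. The SAP states no numerical result for equation (2), so there is no figure of its own to reproduce.

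**Algebra.** Let SE = √Var(log λ̂) and Z = |log λ̂| / SE, so Z ≥ 0.

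- Printed: p = 2Φ(Z). Since Φ(Z) ≥ 0.5, p ≥ 1; as Z grows, p rises towards 2.
- Correct: p = 2[1 − Φ(Z)] = 2Φ(−Z).
- The two sum to 2, so the printed value is 2 minus the correct one.
- Equation (1) excludes 1 when Z > z(1−α/2). This is the same as Φ(Z) > 1 − α/2, and so as 2[1 − Φ(Z)] < α. At α = 0.05 the printed value then exceeds 2 − 0.05 = 1.95.

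**Values.**

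| Z | 2Φ(Z), printed | 2[1 − Φ(Z)] |
|---|---|---|
| 0 | 1.000 | 1.000 |
| 0.5 | 1.383 | 0.617 |
| 1 | 1.683 | 0.317 |
| 1.96 | 1.950 | 0.050 |
| 2.576 | 1.990 | 0.010 |
| 3 | 1.997 | 0.0027 |

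**Worked examples.** The event counts are assumptions for illustration. Each arm has 335 patients (half of the planned 670), an assumed 335 patient-years, and at most one event per patient. With y events in n patients, S² = [n/(n−1)] × (y/n) × (1 − y/n), so nS²/Y² reduces to (n − y) / [(n − 1)y].

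For 4 against 20 events:

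- Rate ratio = 4/20 = 0.20, and |log 0.20| = 1.609.
- Variance = 331/(334 × 4) + 315/(334 × 20) = 0.2478 + 0.0472 = 0.2949, so SE = 0.543.
- Z = 1.609/0.543 = 2.964.
- 95% interval: 0.20 × exp(±1.96 × 0.543) = 0.069 to 0.580.
- Printed p = 1.997; correct p = 0.0030.

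| Events | Rate ratio | 95% interval (1) | Printed p | Correct p |
|---|---|---|---|---|
| 4 vs 20 | 0.20 | 0.069 to 0.580 | 1.997 | 0.0030 |
| 3 vs 12 | 0.25 | 0.071 to 0.880 | 1.969 | 0.031 |
| 5 vs 10 | 0.50 | 0.172 to 1.450 | 1.798 | 0.202 |

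**Agreement with the interval.** Over 100,000 random pairs of log rate ratio (normal, mean 0, SD 1.5) and SE (uniform, 0.05 to 1.5), the 95% interval excluded 1 in 37,828. The printed p was below 0.05 in none of these. The corrected p agreed with the interval in all 100,000.

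**The case against.** **It may not be an error in the SAP.** The printed form differs from 2Φ(−Z) by a single minus sign. The text examined was extracted from a PDF, and similar marks appear to be missing elsewhere in it: the subtraction between the two dates in the exposure formulas (SAP Section 4.6.1), and the dash in the middle eGFR category (SAP Section 4.7.2). This stands as a reason to check the source PDF first. It does not dispose of the point, because minus signs survive in the other typeset formulas of Appendix 8, including the lower limit of equation (1) just above equation (2).

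**A reader might infer that the sparse-event comparison can never show a difference, or that a real imbalance in severe hypoglycemia would be reported as non-significant.** The documents do not support that. Equation (1) is correct and Section 4.1 requires the interval; in the first two worked examples it excludes 1. The printed formula also exceeds 1 for every rate ratio other than exactly 1, so it would fail visibly on almost any data and would probably be caught. Severe hypoglycemia has further cover: logistic regression of incidence (Section 4.6.3.1), and a risk-difference summary and event listing (Section 4.6.2.1.1).

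**The scope is narrow.** Negative binomial regression remains the planned rate analysis, and Appendix 8 applies only when events are too few for it. The gatekeeping in SAP Section 2.1 covers only HbA1c noninferiority and superiority. All of this stands and limits the severity, but it does not make the printed formula right.

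**Conclusion.** As printed, equation (2) is not a valid p-value: it can never fall below 0.05, and it disagrees with interval (1) whenever that 95% interval excludes 1. This follows from the algebra for any data with at least one event in each arm, so that the log rate ratio and its variance exist. The illustrative counts are not needed for it.

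The severity is minor. The fault is confined to one p-value in a conditional fallback for the Level 2, Level 3 and Level 2/3 rate comparisons. The interval is unaffected, and no HbA1c conclusion or type I error claim depends on it. A typographical slip is the most likely explanation. The one open assumption is that the source PDF reads the same as the extracted text.

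**What to change.** 1. Check equation (2) in the source PDF. If a minus sign stands before the absolute value inside Φ, no change is needed.
2. If it is as printed, replace it with p = 2[1 − Φ(|log λ̂| / √Var(log λ̂))], or the identical 2Φ(−|log λ̂| / √Var(log λ̂)).
3. Check that the analysis program gives p < 0.05 exactly when the 95% interval (1) excludes 1.

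The cost is a one-line SAP correction and one program check. No endpoint, analysis set or sample size changes.
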